1. INTRODUCTION

1.1 Background information

Neonatal opioid withdrawal syndrome (NOWS) is a subset of Neonatal abstinence syndrome (NAS) and refers to neonatal withdrawal from opioid drugs and can occur in the presence of other drug withdrawal syndromes. In the United States, neonatal withdrawal following in-utero opioid exposure is typically the result of prolonged maternal use and/or abuse of illicit or prescribed opioids during pregnancy. Birth leads to the abrupt cessation of fetal substance exposure and can precipitate acute withdrawal symptoms that can result in severe health complications with prolonged recovery and longer hospitalization. Withdrawal can be both severe and intense, with an estimated 60% to 80% of exposed neonates requiring pharmacological intervention to control symptoms [1][2].

While the signs and symptoms of NOWS are similar to those experienced by adults undergoing acute opiate withdrawal, they present a higher risk to the neonate due to the babies' dependence on others for all aspects of well-being.

NOWS presenting signs include central nervous system hyperirritability (tremors, jitteriness, irritability, hyperactive muscle reflexes, and excessive high-pitched cry), autonomic nervous system deregulation and instability (tachypnea, nasal flaring, hyperphagia, temperature instability, insomnia, sweating, mottled skin, yawning, and sneezing), and gastrointestinal symptoms (diarrhea, vomiting, and poor feeding) [3][4][5]. Seizures are generally rare, although they have been reported occurring in 2% to 11% of neonate cases in the early stage of severe opioid withdrawal [6][7], especially if medical treatment has been delayed. A recent large observational cohort study of Medicaid babies in 46 US States reported an incidence of seizures was 2.7% among the 1705 observed cases of NAS [8]. Neonates with NOWS can also experience weight loss or failure to thrive, which often results from a combination of poor feeding, vomiting, nausea, and diarrhea [4][5]. If left untreated, some cases of NOWS may even lead to death [5]. Some of the less severe signs and symptoms of opiate withdrawal may persist for several months [3].

The onset, duration, and the severity of NOWS are dependent on several factors: the type of opiate exposure, maternal-fetal drug transferability, poly-drug exposure, time and duration of opiate exposure, placental and fetal drug concentrations, the rate of excretion, spatial representation and density of opiate receptors, and gestational age [4][1][9][10].

The management of neonates at risk of this withdrawal syndrome is based on the following [11]:

- Identification of neonates at risk, preferably by identification of maternal substance exposure during pregnancy;
- Early initiation of non-pharmacological care (this first-line treatment provides a suitable, supportive environment for both the mother and baby, which minimizes exposure to stress, and encourages breastfeeding where appropriate);
- Monitoring for signs of withdrawal;
- Pharmacological care, which is instituted when the signs of withdrawal become too severe to be managed with non-pharmacological care

There are no FDA-approved drugs for the treatment of NOWS with or without other concomitant drug withdrawal syndromes; however, there is consensus within the neonatology community that

Clinical Study Code No.: CLI-06563AA1-02	Version No.: 6.0
IND No.: 131,339	Date: 18 March 2021

opioid replacement should be the first-line pharmacotherapy treatment [3][4][12]. Morphine is the most often used opioid for the treatment of neonatal withdrawal following in-utero opioid exposure, followed by methadone, with some hospitals using buprenorphine. While morphine is used in more than 80% of NAS cases requiring pharmacological treatment [11], there is no agreed standard of care [13] or treatment regimens [1][14] and the optimal pharmacological treatment protocols have not been established in large, well-controlled studies.

Commercially available liquid formulations of morphine and methadone are unsuitable for the neonatal population for several reasons. They contain inappropriately high concentrations of opioid, necessitating local compounding of extemporaneous formulations or dilution prior to administration within the hospital pharmacy or by neonatal nursing staff, increasing the risk of medication errors [15][16][17][18]. Commercially available liquid formulations frequently contain alcohol and other preservatives and excipients that are contraindicated or undesirable in the neonatal population. Whilst an alcohol-free morphine solution is available, commercial methadone solutions contain alcohol. Therefore, the currently available pharmacological treatments for Nows leave the neonate at risk of medication errors, other hazards related to local compounding of extemporaneous formulations, and exposure to alcohol, other preservatives, and excipients that are contraindicated or undesirable in the neonatal population.

Buprenorphine has several characteristics that make it an attractive agent in the treatment of Nows. Buprenorphine is a long acting μ -opioid receptor partial agonist and κ -opioid receptor antagonist. The long half-life and duration of action prevents the rapid change in receptor occupancy that can precipitate withdrawal and should allow a simplified dosing regimen to be developed. Sublingual buprenorphine shows a lack of the cardiovascular liability that is associated with methadone. Related to the lack of cardiovascular liability, sublingual buprenorphine possesses a well-established safety profile in adults. Moreover, buprenorphine has the lowest incidence of respiratory depression among opioids, which is dose-dependent and has a ceiling effect in relation to the long half-life of buprenorphine [19][20][21][22].

The CHF6563 development program is intended to develop a neonate-specific formulation of buprenorphine. CHF6563 does not contain ethanol, naloxone, or any excipients considered contraindicated, unsafe, or inappropriate for use in the neonatal population. CHF6563 is intended to control or reduce withdrawal symptoms, decrease duration of treatment, and reduce length of hospital stay in neonates diagnosed with Nows with or without other concomitant drug withdrawal syndromes.

1.2 Study rationale

Chiesi is developing CHF6563 (sublingual buprenorphine) for the treatment of Nows with or without other concomitant drug withdrawal syndromes.

The safety and efficacy of buprenorphine as a treatment for Nows with or without other concomitant drug withdrawal syndromes has been investigated in 5 published studies [23][24][25][26][27] using an extemporaneous formulation containing 30% ethanol. Across the 5 studies, sublingual buprenorphine demonstrated a significant reduction in duration of treatment and stay compared to the standard of care (oral morphine or methadone). The extemporaneously prepared ethanolic buprenorphine sublingual formulation was generally well tolerated in the target population and demonstrated a similar safety profile to oral morphine.

The CHF6563 development program is focused on finding an appropriate, safe, and efficacious buprenorphine formulation, and establishing a buprenorphine-dosing regimen that provides effective control of the clinical signs of Nows when non-pharmacological therapy has failed. The PK profile of buprenorphine should enable a dosing regimen to be developed that will increase the

Clinical Study Code No.: CLI-06563AA1-02	Version No.: 6.0
IND No.: 131,339	Date: 18 March 2021

interval between doses compared with morphine and simplify the weaning regimen, potentially bringing safety and efficacy benefits to the neonate, their families, and healthcare systems.

This study will evaluate the efficacy and safety of a model-derived CHF6563 dosing regimen as a treatment for NOWS with or without other concomitant drug withdrawal syndromes when non-pharmacological therapy has failed.

1.3 Risk/benefit assessment

Sublingual buprenorphine shows a lack of the cardiovascular liability that is associated with methadone. Related to the lack of cardiovascular liability, sublingual buprenorphine possesses a well-established safety profile in adults. Moreover, buprenorphine has the lowest incidence of respiratory depression among opioids, which is dose-dependent and has a ceiling effect in relation to the long half-life of buprenorphine [19][20][21][22].

Buprenorphine is a long-acting, partial μ -opioid receptor agonist and κ -opioid receptor antagonist. Due to its favorable pharmacological characteristics of long half-life and duration of action, buprenorphine has been shown to significantly reduce the median duration of treatment and a median length of stay when compared to morphine and methadone in both retrospective and in RCT study [23][24][25][26][27]. The long half-life and duration of action prevents the rapid change in receptor occupancy that can precipitate withdrawal seen with shorter acting opioids (i.e. morphine). In contrast to the full μ -opioid agonists (morphine and methadone) commonly used to treat Nows, increasing buprenorphine serum concentration results in a ceiling effect for important opioid agonistic side effects, namely respiratory depression (morphine and methadone) or cardiovascular liability including QTc interval prolongation (methadone) [19][20][21][22]. In Kraft's 2017 study, a model based analysis demonstrated that at any time during treatment the mean respiratory rate in morphine treated infants was lower by 4.4 breaths per minute (95% Cl: 0.7, 8.1; p=0.020) as compared to buprenorphine treated infants in the same strata. Although all the respiratory rates recorded were within the normal range, these data suggest a possible safer profile for buprenorphine. In this same study, 13 adverse events occurred in 7 infants in the buprenorphine group and 10 events in 8 infants in the morphine group (P = 0.79 for the no. of events by Fisher's exact test) [28]. Cough, tachycardia, umbilical granuloma, involvement of skin conditions and of gastrointestinal conditions have been observed. There were two serious adverse events. One was an inguinal hernia repair in the morphine group, and one was a supraglottoplasty associated with the Pierre Robin syndrome in the buprenorphine group. There were no elevations in levels of alanine aminotransferase or aspartate aminotransferase in any infant.

The results of the available toxicology studies showed that buprenorphine possess less adverse reactions over other opioids. Single and repeated dose of buprenorphine significantly decreased adverse clinical observations associated with opioid withdrawal. Main acute toxic signs in animals associated with buprenorphine treatment were CNS and cardiorespiratory depression. Subchronic toxicity studies of buprenorphine in rat, dog and monkey showed decreased body weight, inflammatory reaction at the injection site, and clinical biochemistry and hematology parameters changes that reflect this inflammatory reaction. No adverse findings were observed during histology. Positive findings were noted in few genotoxicity assays and an increased incidence of testicular interstitial cell tumors was observed in rats. No effects on fertility and no teratogenic effects were noted, although some developmental effects were observed. During a 4 weeks study in

Clinical Study Code No.: CLI-06563AA1-02	Version No.: 6.0
IND No.: 131,339	Date: 18 March 2021

juvenile rats transient increased activity, excessive behaviors and decreased body weight were noted[29][30][31][32][33][34][35][36][37].

Considering the safety profile of the treatments, the measures in place to ensure the patients' safety and the expected scientific value, the overall risk/benefit assessment can be considered acceptable for the proposed trial.

This trial will be conducted in compliance with the Declaration of Helsinki (1964 and amendments) current ICH E6 Good Clinical Practices and all other applicable laws and regulations.

2. STUDY OBJECTIVES

2.1 Primary Objective(s)

- To assess the efficacy of CHF6563 in babies with NOWS
- To assess the safety and tolerability of CHF6563 in babies with NOWS

2.2 Secondary Objective(s)

- To investigate the pharmacokinetics of CHF6563 in babies with NOWS
- To assess the use of the adjunctive therapy for NOWS

3. STUDY DESIGN

This is a randomized, multicenter, double blind, double-dummy, parallel group, controlled study. Fifty-seven neonates with neonatal opioid-withdrawal syndrome (NOWS) with or without other concomitant drug withdrawal syndromes will be randomized to receive CHF6563 or morphine treatment. In order to maintain the blind, a double-dummy design will be used so that the subjects will receive either CHF6563 and morphine matched placebo, or morphine treatment and CHF6563 matched placebo.

The weaning period requires a lower number of weaning steps for CHF6563 compared to morphine. In order to avoid maintaining babies randomized to CHF6563 in the hospital following completion of study drug, only to receive placebo for several days (about 5, depending on the severity of the withdrawal), the unblinded pharmacist will advise the clinical staff that the baby has completed active study treatment following the last active dose of CHF6563 and babies will be eligible for discharge (at least insofar as the clinical trial is concerned) 48 hours after the last active dose. Since the cessation dose will not occur at the same weaning step for the 2 treatment arms, it will be possible to ascertain the treatment for each baby after the weaning step which corresponds to the cessation dose of CHF6563. This is considered a "functional unblinding" since, after this point, it will be possible for members of the blinded team to ascertain the treatment arm.

Prior to the last scheduled dose of CHF6563, all members of the blinded study team will remain completely blinded. Following the last scheduled dose of CHF6563/placebo, members of the blinded study team will not have access to the explicit treatment codes, but it will be possible to ascertain the treatment arm. Similarly, data review will occur without access to explicit treatment codes, since the explicit treatment codes will be maintained in a confidential manner. The randomization list and explicit treatment codes will be disclosed to blinded study team members only after the database is locked.

Clinical Study Code No.: CLI-06563AA1-02	Version No.: 6.0
IND No.: 131,339	Date: 18 March 2021

Withdrawal signs will be assessed using a predefined Finnegan Neonatal Abstinence Scoring Tool (FNAST). FNAST assessments will commence in neonates who show signs of withdrawal despite appropriate non-pharmacological care and recorded every 4 hours (± 1 hour). Pharmacological treatment will start up to 7 days after delivery in neonates who show signs of NOWS (sum of 3 consecutive FNAST scores ≥ 24 or a single score ≥ 12) and have failed to respond to non-pharmacological care. After FNAST assessment has started, it should continue for at least 24 hours, even in case the baby is not randomized.

According to a randomization algorithm, neonates will be assigned to one of the two arms:

- *Test arm*: babies will receive a sublingual dose of CHF6563 at a starting dose of 10 $\mu\text{g}/\text{kg}$ every 8 hours (± 1 h) (using birth weight which should be rounded to the second decimal place) and the corresponding oral dose of morphine matched placebo q4.
- *Reference arm*: babies will receive an oral dose of morphine at a starting dose of 0.07 mg/kg every 4 hours (± 1 h) (using birth weight which should be rounded to the second decimal place) and the corresponding sublingual dose of CHF6563 matched placebo q8.

Pharmacological treatment consists of the following phases; initiation, escalation, stabilization, weaning and cessation. Assessment of the need for treatment and dose adjustments will be based upon clinical signs of withdrawal evaluated using a FNAST and continued until at least 48 hours after the last dose of opioid treatment. A review of the drug dose will take place on a daily basis or more frequently during the escalation phase to ensure timely dose adjustment.

The duration of follow up will be for 6 weeks after the final opioid treatment dose. Evidence of recurrence of significant withdrawal will be monitored for all babies who remain within the hospital. For babies discharged following the required period of inpatient observation (48 hours post last opioid treatment dose), daily telephone contact with the primary caregiver (parental/legal guardian or foster mother) will continue for the first 7 days and will record the baby's wellbeing and identify any escalation of withdrawal signs.

Thereafter weekly telephone contact will continue for the duration of the follow up period. The first weekly telephone contact will occur 7 days after the last daily phone call. Significant escalation of withdrawal signs will warrant clinical review and assessment for relapse severe enough to require pharmacological treatment and readmission.

The end of the trial is defined as the last follow-up at 6 weeks contact of the last subject in the trial.

An 18-month (± 1 months) follow-up visit to assess neurodevelopmental and general health status and confirmation of the safety of the test treatment will be undertaken by the participating centers. This assessment will be evaluated separately from the main part of the study.

4. SUBJECT SELECTION CRITERIA

4.1 Subject Recruitment

57 neonates with neonatal opioid-withdrawal syndrome (NOWS) with or without other concomitant drug withdrawal syndromes will be randomized.

Clinical Study Code No.: CLI-06563AA1-02	Version No.: 6.0
IND No.: 131,339	Date: 18 March 2021

4.2 Inclusion Criteria

Neonates must meet all of the following inclusion criteria to be eligible for randomization into the study:

1. Written informed consent obtained by parents/legal representative (according to local regulation) prior to or after birth.
2. Birth weight \geq 3rd centile for gestational age (GA), according to the CDC growth chart
3. Gestational age \geq 36 weeks
4. Exposure to opioids during the last month before delivery
5. Signs of neonatal opioid withdrawal syndrome requiring treatment, and the sum of 3 consecutive FNAST scores is \geq 24 or a single score \geq 12

4.3 Exclusion Criteria

The presence of any of the following will exclude a subject from study randomization:

1. Familial history of prolonged QTc syndrome
2. Major congenital malformations or evidence of congenital infection
3. Signs of fetal alcohol spectrum disorders
4. Maternal alcohol abuse, defined as average of 3 or more drinks per week in the last 30 days
5. Medical illness at the time of randomization, including but not exclusively:
 - a) Neonatal hypoglycemia requiring intravenous glucose therapy
 - b) Neonatal respiratory illness requiring non-invasive or invasive respiratory support
 - c) Neonatal encephalopathy (including hypoxic ischemic encephalopathy or seizures)
 - d) Severe hyperbilirubinemia—bilirubin at or above the exchange transfusion threshold as defined by the AAP
 - e) Severe elevation of serum aminotransferases (more than twice the upper limit of the age appropriate aminotransferases reference range of the investigational site).
 - f) Proven or suspected early onset neonatal infection which will require more than 48hours treatment with antibiotics
6. Unable to tolerate an oral or sublingual medication
7. Need for medications forbidden in this study protocol
8. Any condition that, in the opinion of the Investigator, would place the neonate at undue risk
9. Participation in another clinical trial of any medicinal product, placebo, experimental medical device or biological substance conducted under the provisions of a protocol on the same therapeutic target. The participation in studies involving diagnostic devices or treatments for conditions other than Nows and Nas may be permitted following an agreement with the Sponsor. Non-interventional observational studies are allowed

Clinical Study Code No.: CLI-06563AA1-02	Version No.: 6.0
IND No.: 131,339	Date: 18 March 2021

More details on the characteristics of mothers whose babies are allowed to be recruited are provided in [section 0](#) and in [APPENDIX 2 – Maternal Screening Questionnaire](#).

4.4 Subject Withdrawal

Babies must be discontinued from the study for any of the following reasons:

- An adverse event occurs that, in the opinion of the investigator, makes it unsafe for the subject to continue in the study
- Additional drug therapy is required when withdrawal signs as assessed by the FNAST are not controlled with the maximum dose of the study drug in combination with phenobarbital.
- Prolonged requirement for opioid therapy defined as > 10 weeks (> 70 days) i.e. inability to wean from opioid therapy.
- The baby is lost to follow-up.
- Parents or legal guardian withdraws consent.
- The baby's safety is affected by use of not-permitted concomitant medication.
- The baby transfers to another inpatient facility during the phase of administration of study drug
- The sponsor or the regulatory authorities or the Ethics Committee(s), for any reason, terminates the entire study, or terminates the study for this trial site or this particular subject.

It is understood by all concerned that an excessive rate of withdrawals can render the study uninterpretable; therefore, unnecessary withdrawals of subjects should be avoided.

However, should a baby discontinue study medication, data collection will continue and all efforts will be made to complete and report the observations as thoroughly as possible.

In case of withdrawal, the Investigator must fill in the “Study Termination” page in the eCRF, reporting the main reason for withdrawal.

If a baby is withdrawn/drops-out of the study after receiving the test treatment, the subject study number and corresponding test treatments should not be reassigned to another subject.

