	
will include treatment (CHF6563 and morphine) as a fixed effect, primary feeding method (formula / any maternal breast milk), maternal primary opioid use (buprenorphine/methadone/other), and concurrent maternal use of benzodiazepines, antidepressants or gabapentin (polypharmacy [yes/no]) as covariates. In cases where observed primary feeding method during the treatment period (formula / any maternal breast milk) differs from the feeding method at time of randomization, the observed primary feeding method will be used for analysis. The adjusted ratio of geometric means between treatments, its 95% CI and associated p-value will be estimated by the model. Babies who discontinue study medication prior to end of the study treatment will be allowed to remain in the study and receive standard of care according to clinical practice. Handling of such cases will be described in the SAP. Babies who discontinue completely (including withdrawal due to treatment longer than 10 weeks) will be imputed using the maximum of the observed value (10 weeks for patients withdrawn due to treatment longer than 10 weeks) or the value of the 90th percentile of duration of any subject completing the study, regardless of treatment group.
 
Secondary efficacy analyses:
 
In cases where observed primary feeding method during the treatment period (formula / any maternal breast milk) differs from the feeding method at time of randomization, the observed primary feeding method will be used for analysis.
 
Time to first weaning (hours) An ANCOVA model based on log-transformed data will be performed to test the treatment effect as time to first weaning (hours). The model will include treatment (CHF6563 and morphine) as a fixed effect, primary feeding method (formula / any maternal breast milk), maternal primary opioid use (buprenorphine/methadone/other), and maternal use of benzodiazepines, antidepressants or gabapentin (polypharmacy [yes/no]) as covariates. The adjusted ratio of geometric means between treatments, its 95% CI and associated p-value will be estimated by the model.
 
Requirement for adjunctive drug therapy (phenobarbital) for signs of NOWS (yes/no) during the treatment period will be analyzed using logistic regression. The Odds ratio and corresponding 95% CI and p-value will be presented, adjusting for primary feeding method (formula / any maternal breast-milk), maternal primary opioid use (buprenorphine/methadone/other), and maternal use of benzodiazepine, antidepressants or gabapentin (polypharmacy [yes/no]).
 
Total hours of treatment with adjunctive therapy will be analyzed using an ANCOVA model. The model will include treatment (CHF6563 and morphine) as a fixed effect and primary feeding method (formula/any maternal breast-milk), maternal primary opioid use (buprenorphine/methadone/other), and maternal use of benzodiazepine, antidepressants or gabapentin (polypharmacy [yes/no]) as covariates. Babies not requiring adjunctive therapy will be included with a value of 0.

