- Regular follow up will continue both before and after discharge from hospital to identify those babies who suffer recurrence of significant withdrawal. The duration of follow up will be for 6 weeks after the final opioid treatment dose. Evidence of recurrence of significant withdrawal will be monitored for all babies who remain within the hospital. **For babies discharged following the required period of in-patient observation (48 hours post last opioid treatment dose), daily telephone contact with the primary caregiver (parental/legal guardian or foster mother) will continue for the first 7 days and will record the infant's wellbeing and identify any escalation of withdrawal signs.** Thereafter weekly telephone contact will continue for the duration of the follow up period.

A 18-months (\pm 1 months) follow-up visit for a further long-term assessment and confirmation of the safety of the test treatment.

The study plan and scheduled tests are summarized in the following table:

			Treatment Period		End of treatment	Follow Up	
	Pre-screening (Mother)	Screening (neonates)	Randomization up to stabilization	Weaning up to end of treatment	48h±4 h after last dose	Up to 6 weeks	18 months
Informed consent forms ^{1,2}	✓ ²						
Questionnaire	✓						
Maternal urine toxicology data (optional)	✓						
Baby toxicology data (optional)		✓					
Inclusion and exclusion criteria		✓	✓ ³				
Gestational Age, sex and race/ ethnicity		✓					
Weight		✓	✓	✓	✓		✓
Length		✓			✓		✓
Head circumference		✓			✓		✓
Randomization			✓				
Vital signs ⁴		✓	✓	✓	✓		
NOWS scores ⁵		✓	✓	✓	✓		
Escalation of withdrawal signs						✓	
hematology and blood chemistry (data recorded)		✓					
Liver Function ⁶			✓ (x2)		✓		
PK CHF6563 ⁷			✓	✓			
Medical history		✓					
Concomitant medications/procedures		✓	✓	✓	✓	✓	
Drug administration			✓	✓			
Cognitive and behavioral development					✓		✓
Feeding status			✓	✓	✓	✓	
Adverse Events assessment ⁸		✓	✓	✓	✓	✓	
General well-being						✓	
Health status							✓
Environmental / social factors							✓
Assessments of the mother / primary carer using standardized questionnaires							✓

1. Maternal urine toxicology data collection requires the mother to sign a separated Informed Consent form.

2. Informed Consent Form for the baby: this is required prior to screening and can be obtained at several time points i.e. during the last month of pregnancy, following birth, or when the baby shows signs of NOWS.

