12.3 Statistical analysis

A detailed statistical analysis plan will be described in the Statistical Analysis Plan. The plan might be reviewed and updated as a result of the blind review of the data and will be finalized before breaking the blind.

12.3.1 **Descriptive Statistics**

General descriptive statistics for numeric variables will include the n (number of observed values), the mean, the standard deviation, the median, the minimum, and the maximum values. For categorical variables, the number and percent of subjects with a specific level of the variable will be presented.

12.3.2 **Missing data**

Babies for whom the parent/legal guardian wishes to discontinue treatment with study medication will be encouraged (via the parent/guardian) to remain in the study for collection of safety and efficacy data until the patient is discharged from the hospital or consent is otherwise withdrawn. These babies will receive standard of care according to clinical practice but will continue to contribute to study assessments. Handling of such cases will be described in the SAP.

Primary Efficacy Variable: Duration of treatment for babies who discontinue from the study prior to end of study treatment for any reason, including withdrawal due to treatment longer than 10 weeks, will be imputed using for the primary efficacy analysis. The imputed value will be the maximum of:

- the actual value for duration of treatment for the neonate (10 weeks for patients withdrawn due to treatment longer than 10 weeks) or
- the 90th percentile value for duration of treatment of all neonates, regardless of treatment group.

Further details on dealing with missing data, along with the handling of possible outliers, will be described in the Statistical Analysis Plan (SAP). Other critical missing data, if any, will be discussed during the review of the data. Decisions will be fully documented in the Data Review Report.

12.3.3 **Patient demographics and baseline characteristics**

Demographics and baseline variables will be summarized by treatment arm using descriptive statistics for the ITT population.

The following variables will be presented: gestational age, sex, race/ ethnicity, head circumference and percentile, weight and percentile, medical history, concomitant diseases, FNAST scores, primary feeding

CONFIDENTIAL

Clinical Study Code No.: CLI-06563AA1-02	Version No.: 6.0
IND No.: 131,339	Date: 18 March 2021

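### Protocol 4.4 makes study exit, not just drug stop, the rule for several treatment failures, and 12.3.2 ends collection at discharge after parent-requested stops, so scheduled relapse and readmission follow-up may end early

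*Protocol*

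**What the plan says.** Protocol 4.4 lists eight reasons under the lead-in "Babies must be discontinued from the study for any of the following reasons". Three of them really do end observation: loss to follow-up, withdrawn consent, and termination by the sponsor, an authority or an ethics committee. The other five are an adverse event that "makes it unsafe for the subject to continue in the study", withdrawal signs uncontrolled at maximum dose plus phenobarbital, opioid need beyond 10 weeks, non-permitted medication affecting safety, and transfer to another inpatient facility during dosing. Below the list, the same section says that "should a baby discontinue study medication, data collection will continue".

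The synopsis (statistical methods) says "Babies who discontinue completely (including withdrawal due to treatment longer than 10 weeks) will be imputed". Section 12.3.2 applies the imputation to babies who "discontinue from the study prior to end of study treatment for any reason, including withdrawal due to treatment longer than 10 weeks". Just before its imputation rule, the synopsis also lets babies who stop study medication stay in the study on standard of care, with no end point stated.

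For parent-requested drug stops, section 12.3.2 encourages the baby "to remain in the study for collection of safety and efficacy data until the patient is discharged from the hospital", or until consent is withdrawn. Section 3 says "The duration of follow up will be for 6 weeks after the final opioid treatment dose", and section 7.1 says "For babies discharged following the required period of in-patient observation (48 hours post last opioid treatment dose), daily telephone contact" follows for 7 days, then weekly contact. Neither these sections nor 7.1.7 makes an exception for babies who stopped study drug early. Relapse and readmission for relapse are secondary endpoints (8.2, 12.3.5).

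**The concern.** A baby who cannot be weaned in 70 days, or who fails maximum dose plus phenobarbital, normally remains consented and contactable. Needing opioid for longer is no reason to stop observing. These exits are related to outcome, so what goes missing after them would not be missing at random for relapse and readmission. The imputation in 12.3.2 covers duration of treatment only, and the protocol states no rule for relapse or readmission after exit.

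For the 4.4 exits, four items may go uncollected on the planned schedule: relapse, the readmission endpoint field, new non-serious adverse events, and the date and time of the last NOWS dose. That last item is needed for length of opioid-related stay (12.3.5). For parent-requested stops the exposure is mainly to events after discharge; length of stay would normally be known by then.

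SAP 1.2 adds a further tension. It handles additional or alternative therapy by treatment policy, which needs observation after the event, while 4.4 removes babies who need additional therapy beyond phenobarbital. That estimand concerns the primary endpoint, so it shows intent and is not a rule for relapse.

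**Working it through.** **1. The plan's own figure.** Inputs (12.1): difference 13 days, SD 15 days, two-sided 0.05, power 80%, 2:1 allocation. In a two-sample t-test the noncentrality is 13 / (15 × √(1/17 + 1/34)) = 2.92. Power is 81.6% at 17/34 and 79.1% at 16/32, so 51 is the smallest 2:1 total reaching 80%. With 10% withdrawal, 51 / 0.9 = 56.7, rounded up to 57. Both figures reproduce. Planned withdrawals are 57 − 51 = 6 (38 − 34 = 4 CHF6563; 19 − 17 = 2 morphine), or 6/57 = 10.5%, for all reasons together and with no split by reason.

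**2. The rules side by side.**

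| Case | Rule for exit | Rule for continued collection | Result |
|---|---|---|---|
| Opioid need over 70 days | 4.4: leave the study; synopsis and 12.3.2: complete discontinuation | 4.4 sentence on drug stops, but this case is classed as leaving the study | Study exit is the better-supported reading |
| Failure at maximum dose plus phenobarbital; non-permitted medication; transfer | 4.4: leave the study | 4.4 sentence on drug stops | Governing rule not stated |
| Adverse event, drug alone unsafe | 4.4 applies if continuing in the study is unsafe | 4.4 sentence; drug-only stops exist in 7.1.3 and 10.5 | Governing rule not stated |
| Parent-requested drug stop | None | 12.3.2: to discharge; synopsis: may remain, no cut-off; 3, 7.1 and 7.1.7: 6 weeks | Conflict on the end point |

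**3. Expected number over 70 days.** No mean duration is given, so the morphine mean M is assumed to be 20 to 40 days, with the design SD of 15 and CHF6563 13 days shorter. Expected number = 19 × P(morphine > 70) + 38 × P(CHF6563 > 70).

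| M (days) | Normal | Lognormal, same mean and SD |
|---|---|---|
| 20 | 0.01 | 0.56 |
| 30 | 0.08 | 0.87 |
| 40 | 19 × 0.0228 + 38 × 0.0021 = 0.51 | 19 × 0.0423 + 38 × 0.0180 = 1.49 |

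The range is about 0.01 to 1.5 of 57 babies. The M = 20 row is weak: it puts CHF6563 at mean 7 with SD 15, where the normal model places about 32% of durations below zero.

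**4. Contacts after discharge, per baby.** At the earliest permitted discharge (48 hours after the last opioid dose), daily calls fall on days 3 to 9 (7 calls). The first weekly call comes 7 days after the last daily call, giving days 16, 23, 30 and 37 (4 calls). At least 7 + 4 = 11 scheduled contacts therefore come after discharge. This describes the schedule for one baby. It does not measure data lost, because the number of such babies is unknown and could be zero.

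**5. Weight of one baby.** 1/38 = 2.6 percentage points of the CHF6563 arm; 1/19 = 5.3 points of the morphine arm.

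**The case against.** The strongest objection concerns readmission. A reader might infer that collection ending at discharge captures no readmissions. The documents do not support that. An unplanned overnight admission meets the seriousness criterion in 10.1, and 10.8 requires NOWS events that meet the definition to be reported as serious adverse events. Section 10.9, on reporting them to the sponsor, is not in the text available for review, so loss of new serious adverse events cannot be claimed. What stands is narrower: a safety report is not the endpoint field filled from scheduled contacts, and it does not cover relapse without admission.

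Second, the plan already separates drug stop from study stop in the synopsis and in 12.3.2, and the continued-collection sentence in 4.4 can be read as qualifying the list above it. For that reason the second and third rows of the table show ambiguity, not a proven loss. The same reading is possible for the 10-week case, since study drug stops there too and the two supporting texts are imputation rules. But they class these babies as leaving the study completely, which favours exit.

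Third, only one clause, in a missing-data section, mentions discharge, and it covers only parent-requested stops. That is correct. It still contradicts the 6-week follow-up and needs aligning.

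Finally, a baby not yet weaned at exit cannot be assessed for relapse until the last opioid dose is known. This is true, and it is a reason to record that dose.

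**Conclusion.** The point holds as a cheap improvement to the design. Section 4.4 requires study exit for opioid need over 70 days, leaves the governing rule unstated for up to four other reasons, and 12.3.2 sets a discharge cut-off that conflicts with the rest of the protocol. Scheduled collection may stop early for the items named above.

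The size is unknown and probably small: about 0.01 to 1.5 of 57 babies over 70 days, resting on the assumed morphine mean of 20 to 40 days and the design SD. It is tempting to cap the total at the 6 planned withdrawals. That is a planning figure and not a bound; parent-requested stops who remain in the study need not be among the 6, while some of the 6 would be consent withdrawals or losses that no wording can recover. Nor do the documents allow a direction or size of bias to be derived.

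The primary endpoint is unaffected: study exits are imputed under 12.3.2, and duration runs only to the last dose of study drug. Handling of drug stops is deferred to the SAP, and version 1.0 is not available. An SAP could not in any case analyse data that were not collected. The trial stopped at 7 randomized babies, and SAP version 2.0 lists efficacy data without inference (2.2.3, 6.1). The point therefore concerns the plan as designed for 57, with little bearing on the reported results.

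**What to change.** In 4.4, keep consent withdrawal, loss to follow-up, and termination by the sponsor, an authority or an ethics committee as study discontinuation. Make the other five reasons discontinuation of study drug; for adverse events, unless the investigator judges continued follow-up itself unsafe. For these babies, keep the 48-hour assessment where feasible, adverse event collection, and the scheduled contacts to 6 weeks after the last opioid dose given for NOWS, and record the date and time of that dose.

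In 12.3.2, replace the discharge cut-off with the 6-week follow-up contact. Because the imputation there is tied to leaving the study, also state that reclassified babies keep the planned primary-endpoint value: the larger of the actual duration (10 weeks if over 10 weeks) and the 90th percentile. The rules for stopping treatment and the primary analysis do not change.

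The cost is protocol wording and one eCRF split between drug stop and study stop. Each affected baby needs the calls already scheduled for babies who complete treatment (at least 11 at the earliest discharge). Follow-up is longer for babies still on opioid, and data from transferred babies will be incomplete. The sample size does not change.
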